7.1.2.1 Safety Steering Committee

The safety of the patients enrolled in this study will be closely monitored on an ongoing basis by an SSC during dose escalation review meetings. The SSC will review clinical data from the study, including safety, available efficacy and PK data (if available), and will ensure the appropriate selection of doses to be used in the dose escalation and dose expansion phases of the study. All safety data collected up to Cycle 1 Day 21 for each patient will be reviewed.

The SSC will consist of:

- The Sponsor's Study Team Physician or a designee.
- Clinical Research Organization's Medical Monitor, who will chair the committee.
- The Investigators or a designee from every participating site, at least from sites which enroll patients in the respective dose cohort.
- Other Sponsor and Parexel team members.

The SSC charter will define the exact membership and who should be present for recommendations to be made.

For the initiation of a new dose level, the SSC will evaluate the available safety, tolerability and PK data (if available) of NOX66 in combination with EBRT. Once 3 patients have completed their DLT assessment period, the SSC will review and assess all available safety data to make recommendations regarding that dose and/or the next dose/study part. The decisions and decision-making regarding the next dose level will be documented and provided to the Investigators prior to dosing of new patients. The final decision regarding dose escalation or dose de-escalation will be made by the SSC.

The SSC will be responsible for the following:

- Assessment of all available safety, tolerability and exposure data during the study.
- Defining patients who have experienced a DLT per protocol definitions of DLT (see Section 7.1.2.2).
- All recommendations regarding dose escalation or dose de-escalation of NOX66. The SSC may recommend proceeding with dose escalation, expand the current dose level with additional patient enrollment or de-escalate the dose to a lower dose level.
- All recommendations regarding modification of NOX66 dosing schedule, if required. The SSC may recommend adjusting the NOX66 dose, dosing frequency or schedule during either Cycle 1 or subsequent cycles. In this situation, the protocol must be amended.
- All recommendations relating to initiation of Part 2 enrollment.
- Recommendation for cessation of dose escalation.
- The review of safety and tolerability of both doses of EBRT (8 Gy and 20/25 Gy administered as 1 or 5 fractionated doses).
- All recommendations regarding the replacement of any excluded or withdrawn patients on study, if necessary.*
- * Any patient initiated on treatment in error (i.e., because he or she failed to meet inclusion and/or exclusion criteria) but meeting the criteria of an evaluable patient, will be reviewed on a case-by-case basis by the SSC to determine if the patient should be included or excluded in the recommendation for dose escalation.

See Section 7.1.2.2 for details on DLT assessment.

7.1.2.2 Assessment of Dose-limiting Toxicities

A DLT is defined as an AE that occurs during Cycle 1 (Day 1 to Day 21) that is assessed as unrelated to the disease, intercurrent illness or concomitant medications and that, despite optimal therapeutic interventions, meets any of the following criteria (judged to be associated with NOX66 alone or in combination with EBRT [possibly, probably or definitely related to]):

- 1. Grade 3 or higher non-hematological toxicities (excluding alopecia) with the following exceptions:
 - a. Grade 3 nausea/vomiting or diarrhea < 72 hours with adequate antiemetic and other supportive care

- b. Grade 3 fatigue < 1 week
- c. Grade 3 or higher electrolyte abnormality that lasts 24 to 72 hours, is not clinically complicated, and resolves spontaneously or responds to conventional medical drugs
- 2. Grade 4 non-hematologic (non-laboratory) toxicity of any duration.
- 3. Grade 3 or Grade 4 febrile neutropenia of any duration.
- 4. Grade 4 neutropenia or thrombocytopenia > 5 days.
- 5. Grade 3 thrombocytopenia with bleeding.
- 6. Grade 3 thrombocytopenia in combination with a Grade 3 or greater blood and lymphatic system disorder.
- 7. Grade 3 AST or ALT that is associated with a Grade 2 or greater rise in bilirubin that lasted for more than 7 days.
- 8. Any AST or ALT > $8 \times$ ULN regardless of duration (5 to $8 \times$ ULN for up to 2 weeks is allowed).
- 9. Any AE that results in a treatment delay or hold of > 14 days.

Grading of DLTs will follow the guidelines provided by the National Cancer Institute-Common Terminology Criteria for Adverse Events (NCI-CTCAE) v5.0.

All AEs of the grades specified above count as DLTs unless they are clearly and incontrovertibly due to disease progression or extraneous causes.

After all patients enrolled in a cohort complete Cycle 1, and the data from these patients are available, a dose escalation meeting will be conducted. At least 3 evaluable patients are required in order to proceed with DLT evaluation for each cohort.

The criteria for determination of an evaluable patient for a dose escalation decision or determination of the MTD, must include:

- Patient who experienced a DLT during the 21-day treatment cycle (Cycle 1), or
- Patient who has not experienced a DLT and has taken at least 80% of the prescribed daily doses of NOX66 and completed all safety evaluations.

For each dose escalation cohort, additional patients may be enrolled or replaced if a patient discontinues prior to the completion of Cycle 1 for reasons other than safety. Patients who develop a DLT and discontinue treatment will not be replaced.

If a patient develops any DLT during Cycles 2 to 6, these will be considered 'DLT equivalent toxicity' and will be recorded in the eCRF. This information may be considered during SSC review to assess dose escalation.

When a DLT occurs, the site must immediately inform Parexel who will then inform the other sites that a DLT has occurred and evaluate if a second DLT has occurred at any other sites.

Assessment of toxicities and decisions about dose recommendation for Part 1 (dose escalation) will be made during the SSC meeting.

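### Section 7.1.2.2 can both count and allow AST/ALT of 5 to 8 × ULN, and its electrolyte exception omits events shorter than 24 hours

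*Combined protocol and SAP*

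**What the plan says.** Section 7.1.2.2 opens with conditions that every DLT must meet. The event occurs in Cycle 1, is judged at least possibly related to NOX66 alone or with EBRT, is not due to disease, intercurrent illness or concomitant medication, and meets a criterion despite optimal treatment. Nine criteria follow as alternatives, so one is enough.

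- Criterion 1: "Grade 3 or higher non-hematological toxicities (excluding alopecia) with the following exceptions". The exceptions are 1a, "Grade 3 nausea/vomiting or diarrhea < 72 hours with adequate antiemetic and other supportive care"; 1b, "Grade 3 fatigue < 1 week"; and 1c, "Grade 3 or higher electrolyte abnormality that lasts 24 to 72 hours, is not clinically complicated", which must also resolve spontaneously or respond to conventional drugs. AST and ALT are not listed.
- Criterion 7: "Grade 3 AST or ALT that is associated with a Grade 2 or greater rise in bilirubin that lasted for more than 7 days".
- Criterion 8: any AST or ALT above 8 × ULN is a DLT regardless of duration, with the note that 5 to 8 × "ULN for up to 2 weeks is allowed".

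On grading: "Grading of DLTs will follow the guidelines provided by the National Cancer Institute-Common Terminology Criteria for Adverse Events (NCI-CTCAE) v5.0". The section then adds: "All AEs of the grades specified above count as DLTs unless they are clearly and incontrovertibly due to disease progression or extraneous causes". It does not say which criterion governs when two disagree.

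Sections 4.1.1 and 9.4.6.1 refer back to Section 7.1.2.2 and do not settle the matter. Section 9.4.6.1 makes the number of DLTs the Part 1 primary endpoint, used to estimate the MTD and select the RP2D.

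**The concern.** There are two separate drafting defects.

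The first is a clash over AST/ALT. Because the criteria are alternatives, an isolated, attributable Grade 3 transaminase rise is a DLT under criterion 1. Criterion 8 says that part of the range is acceptable for a limited time. Criterion 7, which requires an accompanying bilirubin rise, adds nothing if criterion 1 already counts every Grade 3 AST/ALT.

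The second is an anomaly within one exception. 1a and 1b have only an upper limit on duration, whereas 1c also has a lower one. As written, a shorter electrolyte abnormality is treated more severely than a longer one.

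The escalation rule in Section 4.1.1 acts on single patients. One reclassification turns 0/3 into 1/3, which brings three more patients into the cohort. It can also turn 1/6 into 2/6, which halts escalation and makes the previous dose the MTD. If different sites or meetings apply different readings, DLT counts are no longer comparable between cohorts.

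**Working it through.** The plan gives no figure to reproduce here. The check applies the criteria literally to test cases and then sizes the effect on the 3+3 rule.

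**Are laboratory events within criterion 1?** Yes. Exception 1c would be unnecessary otherwise, and criterion 2 is expressly limited to non-laboratory events while criterion 1 is not.

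**AST/ALT: isolated, attributable, lasting 7 days.** The protocol does not print the Grade 3 limit, so call it L × ULN. The table assumes L = 5 with a normal baseline.

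| Value | Criterion 1 | Criterion 7 | Criterion 8 | Result |
|---|---|---|---|---|
| 4 × ULN | not met | not met | not met | no DLT |
| 6 × ULN | DLT | not met | allowed | conflict |
| 8 × ULN | DLT | not met | allowed | conflict |
| 9 × ULN | DLT | not met | DLT | DLT, no conflict |

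For other values of L, the clash runs from the larger of 5 and L up to 8 × ULN, and it disappears if L is 8 or more. Grading may also differ with a raised baseline, since Section 5.1 admits patients with liver metastasis at up to 5 × ULN. The redundancy of criterion 7 does not depend on L, because both criteria refer to Grade 3.

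**Electrolytes: Grade 3, uncomplicated, resolving, attributable.**

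| Duration | Inside 1c? | Result under criterion 1 |
|---|---|---|
| 12 h | no | DLT |
| 23 h | no | DLT |
| 24 h, 48 h, 72 h | yes | not a DLT |
| 73 h | no | DLT |

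The classification goes from DLT to not a DLT and back to DLT as duration grows.

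**Effect on escalation.** Under Section 4.1.1 a dose passes with 0/3, or with 1/3 followed by 0 of the next 3. With per-patient DLT probability p,

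P(pass) = (1 − p)³ + 3p(1 − p)²(1 − p)³ = (1 − p)³ + 3p(1 − p)⁵.

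The documents give no rate q for disputed events, so q is assumed.

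*No other DLTs (p = q).* If disputed events are not counted, P(pass) = 100%. If they are counted:

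- q = 5%: 0.857 + 0.116 = 97.3%
- q = 10%: 0.729 + 0.177 = 90.6%
- q = 15%: 0.614 + 0.200 = 81.4%

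At q = 10%, the chance of a clean 0/3 is 0.9³ = 72.9%, so about 27% of cohorts would not clear at the first three patients.

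*Undisputed DLT rate 10%, disputed events independent.* P(pass) is 90.6% without the disputed events. With q = 10%, p = 1 − 0.90 × 0.90 = 0.19 and P(pass) = 0.531 + 0.199 = 73.0%. With q = 5% it is 82.4%, and with q = 20% it is 53.6%.

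**The case against.** The strongest reply has four parts.

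*The specific rule displaces the general one.* On this view criteria 7 and 8 govern AST/ALT and criterion 1 covers everything else. This is a natural reading, but the protocol does not state it. It sits badly with criteria that are alternatives and with the closing sentence that all events of the specified grades count. It is fair to add that redundancy alone proves little: criterion 2 lies largely inside criterion 1 as well. The real conflict is the allowance in criterion 8.

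*The opening conditions already remove these events.* Attribution does narrow the field, and an electrolyte change corrected within hours might be said not to persist despite optimal treatment. But 1c itself describes events that resolve or respond to treatment. If the opening conditions removed those, 1c would have no work to do. A reader might infer that the 24-hour bound is a slip, but the text does not say so.

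*The SSC will resolve it.* A reader might infer that the SSC has no latitude, which goes too far. It judges attribution, the closing sentence has its own exclusion for progression and extraneous causes, and the SSC takes the final escalation decision. However, Section 7.1.2.1 has it identify DLTs by the protocol definition. It has no stated authority to choose which criterion governs.

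*Such events may be rare.* This stands as a limit on size. Section 2.3.1 lists Grade 3 hypocalcemia and hypophosphatemia among non-serious Grade 3 events seen in 4 patients, lists no transaminase event, and reports none as related to NOX66. Section 4.2 reports no DLTs in the earlier EBRT study. That experience stops at 1200 mg, and this trial goes to 2400 mg. Section 8.2.7 schedules Cycle 1 laboratory tests on Days 1, 6 and 14, so a duration under 24 hours can be documented only by an unscheduled repeat.

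**Conclusion.** The wording is defective in two limited ways.

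For AST/ALT, attributable values of 5 to 8 × ULN lasting up to 2 weeks are allowed by criterion 8. They are DLTs under criterion 1 to the extent that they are Grade 3 under CTCAE v5.0. A reader might infer that every isolated Grade 3 AST/ALT is caught in the conflict. It is not, since above 8 × ULN criteria 1 and 8 agree.

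For electrolytes, 1c is non-monotonic in duration. A reader might call this a self-contradiction too, but no two sentences conflict. It is an exception with an unexplained lower bound, and on its own it is the lesser of the two.

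A reader might also infer a risk of missed toxicity. The literal reading points the other way: it counts more DLTs than the reading in which the allowance governs. The main risk is needless cohort expansion or an MTD/RP2D set too low. The drop from 100% to 91% in the chance of passing the 3+3 is illustrative. It assumes that disputed events occur in 10% of patients, are all attributed to treatment, and are the only DLTs. The wording defects do not depend on that rate.

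**What to change.** Amend Section 7.1.2.2 so that each event has one classification:

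- Reconcile criterion 1 with criteria 7 and 8 for AST/ALT, and print or cite precisely the grade limits relied on, including the handling of a raised baseline.
- Reconcile the lower bound of the 1c window with the form of 1a and 1b. If the bound is intended, state its purpose and how events shorter than 24 hours are classified.
- State which criterion takes precedence when two apply.

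The sponsor's clinicians should choose the thresholds; none is proposed here. The cost is a few lines of protocol wording in an amendment, with no change to sample size, visits or analysis. If patients have already been assessed, the SSC should record which reading was applied to any affected event.

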2.3.1 Risk Assessment

There was one treatment-emergent adverse event (TEAE), observed in Study NOX66-001A (patients with prostate cancer, BC, ovarian cancer, and lung cancer), of moderate (Grade 2) anemia possibly related to NOX66 when dosed at 800 mg as a monotherapy. In combination with carboplatin the most common TEAEs of mild to severe anemia, neutropenia and hypocalcemia were attributed to carboplatin alone. Of the four deaths occurring during the NOX66-carboplatin treatment, sudden death, in the absence of an autopsy, was conservatively attributed to possibly related to carboplatin and all other deaths were due to disease progression.²

In combination with radiotherapy (Study NOX66-002A [patients with mCRPC]), AEs of mild dry mouth, stomatitis (oral mucositis) and fatigue, observed for patients receiving 400 mg, 800 mg and 1200 mg NOX66, were possibly related to the treatment.²

The majority of all other AEs were mild to moderate (Grades 1 to 2). Excluding serious adverse events (SAEs), Grade 3 AEs were lymphopenia, nausea, vomiting, asthenia, elevated blood alkaline phosphatase, hypocalcemia, hypophosphatemia, back pain and bone pain, and spinal pain which were reported in 4 patients. No Grade 4 AEs were reported. None of these AEs were considered related to NOX66 by the Investigator.

Pathmanandavel et al (2021) and Crumbaker (2020) conducted a Phase 1/2 trial of the combination of $_{177}$ lutetium prostate-specific membrane antigen (PSMA) 617 (LuPSMA-617) in combination with NOX66 in men with end-stage mCRPC. Previous trials of lutetium PSMA in men with mCRPC had demonstrated good safety and efficacy. In this study, patients with mCRPC were administered NOX66 (400 mg to 1200 mg daily for 10 days) in combination with LuPSMA-617. Results showed similar and consistent results when compared with the safety and tolerability profile from other studies. The most frequent AEs were (Grade ≥ 2) anemia (n = 19),

fatigue (n = 9), xerostomia (n = 3), anal inflammation (n = 3), thrombocytopenia (n = 3), constipation (n = 1), and pneumonitis (n = 1).⁴

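### The hematological DLT criteria in Section 7.1.2.2 are not consistent across grades: a short Grade 4 thrombocytopenia can go uncounted where the same picture at Grade 3 is a DLT

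*Combined protocol and SAP*

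**What the plan says.** Protocol Section 7.1.2.2 defines a DLT as a Cycle 1 event (Days 1 to 21) that meets at least one of nine criteria.

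- Criterion 1: "Grade 3 or higher non-hematological toxicities (excluding alopecia) with the following exceptions". Criterion 2: "Grade 4 non-hematologic (non-laboratory) toxicity of any duration". Neither reaches hematological toxicity.
- Criterion 3: "Grade 3 or Grade 4 febrile neutropenia of any duration".
- Criterion 4: "Grade 4 neutropenia or thrombocytopenia > 5 days".
- Criterion 5: "Grade 3 thrombocytopenia with bleeding".
- Criterion 6: "Grade 3 thrombocytopenia in combination with a Grade 3 or greater blood and lymphatic system disorder".
- Criteria 7 and 8 concern transaminases. Criterion 9 takes any adverse event that leads to a delay or hold of more than 14 days.

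The section then states: "All AEs of the grades specified above count as DLTs", unless progression or an extraneous cause is clearly responsible. A patient without a DLT is evaluable only after at least 80% of the prescribed doses and all safety evaluations.

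Under Section 4.1.1, no DLT in 3 patients clears a dose, one in 3 leads to 3 more patients, one in 6 clears the dose, and anything above that halts escalation. Section 9.4.6.1 makes the number of DLTs the Part 1 primary endpoint.

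**The concern.** A toxicity list that drives dose escalation should be ordered by severity: if an event counts, a worse form of the same event should count too. Criteria 3 to 6 do not guarantee this. Section 10.3.3 defines Grade 4 as life-threatening and Grade 5 as death, so what falls between the criteria is more serious than what they name.

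The wording looks unintended. Criterion 1 is open upward from Grade 3, and criterion 6 is open upward for the accompanying disorder, but thrombocytopenia itself is fixed at Grade 3 in criteria 5 and 6.

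At stake is the accuracy of the count on which the MTD and RP2D rest. With cohorts of 3 to 6 patients, one miscounted patient can change the decision.

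**Working it through.** **The plan's own figure.** The only number stated for the size of Part 1 is its maximum of 30 patients. It reproduces as 6 + 3 × 8 = 30 and is not in dispute. No DLT rate or operating characteristic is given, so the check consists of applying the criteria as worded.

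**Step 1: apply the list.** Holds are 14 days or less unless stated.

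| Cycle 1 event | Criterion met | DLT? |
|---|---|---|
| Grade 3 thrombocytopenia, Grade 1-2 bleeding, 3 days | 5 | yes |
| Grade 4 thrombocytopenia, same bleeding, 3 days | none | no |
| Grade 4 thrombocytopenia, same bleeding, 6 days | 4 | yes |
| Grade 4 thrombocytopenia, Grade 3 bleeding, 3 days | 1 | yes |
| Grade 3 thrombocytopenia with Grade 3 anemia | 6 | yes |
| Grade 4 thrombocytopenia with Grade 4 anemia, 5 days | none | no |
| Febrile neutropenia, Grade 4 | 3 | yes |
| Febrile neutropenia, Grade 5 | none | no |
| Grade 4 anemia alone, hold of 10 days | none | no |
| Grade 4 anemia alone, hold of 15 days | 9 | yes |

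Rows 1 and 2, rows 5 and 6, and rows 7 and 8 are the three reversals of order. Row 4 treats the bleeding as a non-hematological event in its own right. The anemia rows show an omission, not a reversal, because no lower grade of isolated anemia is listed.

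**Step 2: who would be counted as having no DLT?** Cycle 1 has 14 dosing days, or 28 doses twice daily.

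- In days, 80% × 14 = 11.2, so 12 days are needed. Missing 3 days leaves 11/14 = 78.6%, which is non-evaluable.
- In doses, 80% × 28 = 22.4, so 23 are needed. At most 5 may be missed (23/28 = 82.1%).
- If dosing stops and does not resume in Cycle 1, the patient stays evaluable only if the first missed dose is the 24th or later, which is the evening of Day 12.

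Section 6.6 holds NOX66 for related events above Grade 1 (anal or perianal rash excepted). An early Grade 4 cytopenia therefore usually makes the patient non-evaluable rather than a counted non-DLT. The miscount is left mainly for events from about Day 12 to Day 21 and for holds of no more than 5 doses.

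**Step 3: does criterion 9 close the gap?** Days 8 to 21 inclusive are 14 days. Even if rest days count toward a hold, one that starts on Day 8 or later has not exceeded 14 days by Day 21, the limit of the data that the Safety Steering Committee (SSC) reviews under Section 7.1.2.1. The late events of Step 2 are therefore not caught by that date.

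**Step 4: effect on the decision.** One uncounted evaluable patient turns 1/3 into 0/3, so the dose is cleared instead of being tested in 3 more patients. It turns 2/6 into 1/6, so the dose is cleared instead of escalation being halted.

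**The case against.** The strongest reply is that no committee would ignore a Grade 4 thrombocytopenia with bleeding. The SSC reviews all Cycle 1 safety data and makes the final escalation decision (Section 7.1.2.1). Enrollment pauses after 3 patients until it clears the dose. Section 7.1.2 blocks escalation where the Section 7.1.1 stopping criteria are met, and these include unacceptable toxicity. This stands as protection for patients. It does not repair the endpoint: the SSC must identify DLTs by the protocol's definitions, unacceptable toxicity is not defined, and stopping by judgement leaves the DLT count unchanged.

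Two stronger readings are tempting, and the documents do not support them.

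- **A reader might infer that a fatal hematological event can simply clear a dose.** A patient who dies having taken under 80% of doses is non-evaluable, a death recorded as a non-hematological event falls under criterion 1, and the SSC can stop. What remains is undefined status: Section 7.1.2.2 allows replacement only for reasons other than safety, and does not say how a death or safety stop that meets no listed criterion is handled. A death on Days 15 to 21 might still leave an evaluable patient.
- **A reader might infer that the list is blind to the toxicity that earlier data point to, because anemia has no criterion.** Section 2.3.1 reports a single case of "moderate (Grade 2) anemia possibly related to NOX66 when dosed at 800 mg as a monotherapy". The 19 anemia events of Grade 2 or higher came from a combination with a lutetium radioligand, and anemia with carboplatin was attributed to carboplatin alone. In the earlier EBRT study, the events possibly related to treatment were dry mouth, stomatitis and fatigue, and Section 4.2 reports no DLTs. Anemia can also count through criteria 6 and 9. The omission is a clinical choice that contradicts nothing in the documents; it is only fair to ask whether it was intended.

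**Conclusion.** The inconsistency is real on the text. Grade 4 thrombocytopenia of 5 days or less, with Grade 1-2 bleeding or with a second blood disorder of at least Grade 3, meets none of the severity criteria, although the same picture at Grade 3 does. Criterion 3 stops short of Grade 5. The conclusion rests on a literal reading of the grades, which the section's own back-reference to specified grades invites.

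The scope is limited to evaluable patients, so mainly to late events and short holds, and to events without a hold of more than 14 days. Any probability that a dose is wrongly cleared would need assumed event rates and assumed shares of uncounted events; the documents supply neither, so none is given. The firm statement is that one such patient is enough to move a cohort from 1/3 to 0/3, or from 2/6 to 1/6. This should be fixed because the count is the Part 1 primary endpoint. It is not a sign that the escalation lacks safeguards.

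**What to change.** The sponsor's clinical team should:

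1. Reconcile criteria 3 to 6 of Section 7.1.2.2, so that the list does not count a milder event while leaving a worse form of the same event uncounted.
2. Reconcile the list with the evaluability and replacement text in the same section, stating how a patient is classified who stops or dies for safety reasons without meeting a listed criterion.
3. Confirm whether the absence of an anemia criterion is intended.
4. Re-read any cohorts already cleared against the reconciled list.

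The grades, durations and any anemia threshold are for the clinical team to set. The cost is a few lines in a protocol amendment and the SSC charter. The downside is that slightly more events may count as DLTs, so a cohort may expand to 6.
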